5. TREATMENTS ADMINISTERED

Neflamapimod 40 mg capsules or matching placebo capsules will be administered orally, BID or TID with food for 16 weeks. Subjects will follow the BID regimen if weighing <80 kg or the TID regimen if weighing ≥80 kg.

Furthermore, all subjects will be administered 1 capsule, BID or TID, with food:

- Subjects following the BID regimen will receive one 40 mg neflamapimod capsule or one placebo capsule to be taken twice daily with food (i.e., with the morning and evening meals);
- Subjects following the TID regimen will receive one 40 mg neflamapimod capsules or one placebo capsule to be taken three times daily (i.e., with the morning, mid-day, and evening meals).

Doses must be taken within 30 minutes following a meal or snack. Doses should be taken at approximately same times each day throughout the study and at least 3 hours apart.

The first dose of study drug in each treatment period will be administered at the study center.

The Investigator or other designated, qualified site personnel should review dosing instructions with the subject. Subjects will be instructed to return all study containers, regardless of whether empty or containing unused study drug.

If a subject misses 1 study drug dose (i.e., 1 capsule), the subject should resume dosing at the next scheduled administration time, at which time both the missed dose and the current dose (i.e., 2 capsules) are to be taken. If the subject misses 2 study drug doses (i.e., 2 capsules), the subject should take 2 doses (i.e., 2 capsules) at the next scheduled administration time. Subjects may not take more than 2 doses (i.e., 2 capsules) at any given administration time.

5.1. Packaging and Labeling

EIP Pharma will supply placebo or neflamapimod capsules via blister packs on an individual subject basis.

Both neflamapimod and placebo capsules are opaque in color. Label details will be in accordance with local and national requirements.

5.2. Study Drug Supply, Storage, and Handling

Study drug will be supplied to the site on an individual subject basis. Both neflamapimod and placebo capsules are opaque in color. Study drug is labeled in accordance with local and national requirements.

Neflamapimod capsules should be stored at room temperature.

While at the clinical site, study drug access should be limited to the Investigator and other qualified site personnel.

5.3. Drug Accountability, Disposal, Return, or Retention of Unused Study Drug

The site designated pharmacist or other qualified personnel will document receipt from Sponsor, dispensing to subjects, and return to the study center from subject on the drug accountability log(s).

Subjects will be instructed to return all blister packs to the study center, regardless of whether empty or containing unused study drug. EIP Pharma or designee will review accountability records throughout the conduct of the study.

The site should maintain all study drug containers (used and unused) until final review of accountability is conducted by the EIP Pharma or designee, and instructions regarding return or disposal, as applicable, are provided.

5.4. Method of Assigning Subjects to Treatment Group

After subjects have completed the Screening Visit and are deemed eligible, they will be randomized on a 1:1 basis in a blinded manner to receive either placebo or 40 mg neflamapimod utilizing an automatically generated random code. Randomization will be stratified by ISLT Total Recall score at Baseline (≤ 21 vs. > 21), i.e. by wheter patients have an episodic memory defect at baseline or not. Randomization and stratification will be administered via Interactive Response Technology (IRT).

Subjects will follow the BID regimen if weighing <80 kg or the TID regimen if weighing ≥80 kg.

Study drug for the entire 16-week period will then be sent on a per subject basis to the site.

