6. STUDY ASSESSMENTS AND PROCEDURES

6.1. Schedule of Assessments

The schedule of assessments is presented in Table 6-1.

Table 6-1: Schedule of Assessments

	Study Period / Week / Study Day								
								Early	Follow-
	Screening		7	Freatmen	t Period			Termination	Up
	Screening Visit ^a	Baseline	Week 2	Week 4	Week 8	Week 12	Week 16	ET Visit ^e	Follow- Up Visit ^d
Assessment	Within 21- 35 days of D1	D1 ^b	D14	D28	D56	D84	D112	Within 3 days after last dose	Within 14 days (±3) of last dose
Informed Consent	Xe	DI:	(±3)	(±3)	(±5)	(±5)	(±5)		iast dose
	X								
Medical history review	X X ^f								
Pregnancy testing	X						v	v	v
Physical examination ^g Vital signs ^h	X	X	X	X	X	X	X	X	X
Hematology and	X	X	Λ	X	X	X	X	X	Λ
chemistry ⁱ	Λ	A		Λ	Λ	Λ	Λ	Λ	
Coagulation studies ⁱ	X				X				X
12-lead electrocardiogram ^j	X								
DaTscan TM , if needed	X^k								
CT/MRI	X¹								
C-SSRS	X	X		X	X	X	X	X	
MMSE ^m	X	X			X		X	X	
NTB ^m , International Shopping List Test (ISLT)	X	X		X	X		X	X	
CDR-SB		X			X		X	X	
NPI-10	X	X		X	X		X	X	
Timed Up and Go (TUG)		X			X		X	X	
EEG ⁿ		X					X	X	
Dispense study drug		X	X	X	X	X			
Pharmacokinetic sampling ^o			X	X	X				
Plasma sample for protein biomarker testing ^p	X^q	X					X	X	

	Study Period / Week / Study Day								
	Screening	Treatment Period						Early Termination	Follow- Up
	Screening Visit ^a	Baseline	Week 2	Week 4	Week 8	Week	Week 16	ET Visit ^e	Follow- Up Visit ^d
	Within 21-							Within 3 days after	Within 14 days
Assessment	35 days of D1	D1 ^b	D14 (±3)	D28 (±3)	D56 (±5)	D84 (±5)	D112 (±5)	last dose	(±3) of last dose
Prior/concomitant medication	X	X	X	X	X	X	X	X	X
Adverse event recording	X	X	X	X	X	X	X	X	X
Final study drug reconciliation							X	X	

CDR-SB: Clinical Dementia Rating Scale – Sum of Boxes; C-SSRS: Columbia-Suicide Rating Scale; CT: Computed tomography; D=day; MMSE: Mini-Mental State Examination; MRI: Magnetic resonance imaging; NPI-10: 10-item Neuropsychiatric Inventory; NTB: Neuropsychological Test Battery.

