- a. One to two Screening visits are planned during which safety screening procedures are to be completed and reviewed, including a practice NTB and the required diagnostic and cognitive impairment procedures. Screening will be conducted within 21 days before Baseline (Day 1); if a DaTscan and/or MRI or CT scan is required to determine study eligibility, Screening may be extended to 35 days. (If necessary, a second visit may be conducted on a different day to allow for scheduling purposes.) All screening assessments should be conducted within 21-35 days of Day 1 and can be condensed to one visit
- b. On Day 1, all procedures should be conducted prior to first dose of study drug.
- c. Subjects who prematurely discontinue study drug for any reason will be asked to return to the study center for an Early Termination visit within 3 days following the last study drug dose; if it is determined that the subject will discontinue study drug while at the study center for a scheduled visit, then the Early Termination visit should be conducted at that time.
- d. The Follow-up Visit should be conducted within 14 (±3) days of the last dose of study drug for subjects who complete the study or discontinue early.
- e. Informed consent procedures, including signing of informed consent, must be completed before any study-specific procedures are performed.
- f. Female subjects who have reached menopause in the previous year must have a serum or urine pregnancy test performed during Screening; subjects with positive results are not eligible for study participation.
- g. Refer to Section 6.2.8 for details regarding physical examination.
- h. Vital signs include blood pressure, pulse, respiratory rate, and body temperature. Vital signs should be measured after the subject has been in sitting position for 5 minutes.
- i. Details of clinical laboratory sampling for chemistry, hematology, and coagulation studies are discussed in Section 6.2.10.
- j. Details of 12-lead ECG assessment are discussed in Section 6.2.9.
- k. Subjects are required to have a prior DaTscan. If a DaTscan has not been performed within the previous 2 years, it is to be performed during Screening only after subject has been deemed eligible based on all other inclusion/exclusion criteria (e.g., medical history, laboratory testing) and prior to randomization. Note that if DaTscan results are negative (i.e., no evidence of

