6.2.4. Cognitive Function Tests

Cognitive function tests include a Neuropsychological Test Battery (NTB) as well as the Letter Fluency Test and Category Fluency Test (CFT), which are all components of the primary objective/endpoint to assess attention, executive function, and visuospatial function.

Cognitive function tests to be performed as components of the secondary objective include the CDR-SB, MMSE, NPI-10, Timed Up and Go (TUG), and International Shopping List Test (ISLT).

At Baseline and on any visits at which both NTB and other cognitive tests are conducted, the NTB should be performed prior to the other tests.

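### Does shipping study drug only after randomization clash with stratifying on the Day 1 ISLT score and dosing the same day?

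*Protocol*

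**What the plan says.** Section 5.4 opens by placing randomization after the Screening Visit, once the subject is found eligible. It then says "Randomization will be stratified by ISLT Total Recall score at Baseline", with the cut at 21, and assigns both randomization and stratification to the IRT. After the weight rule it adds: "Study drug for the entire 16-week period will then be sent on a per subject basis to the site". The Synopsis and Sections 3.1.2 and 3.2 name the same stratum.

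Sections 3.1.1 and 3.1.2 date Baseline as Day 1, and the ISLT is given both at Screening and on Day 1. Section 3.1.2 starts dosing on Day 1 after the baseline procedures. Footnote b of Table 6-1 agrees: "On Day 1, all procedures should be conducted prior to first dose of study drug". Section 5 adds: "The first dose of study drug in each treatment period will be administered at the study center". The row "Dispense study drug" in Table 6-1 is marked at Baseline and at Weeks 2, 4, 8 and 12.

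On supply, Section 5.1 says "EIP Pharma will supply placebo or neflamapimod capsules via blister packs on an individual subject basis" and Section 5.2 says "Study drug will be supplied to the site on an individual subject basis". Neither describes stock held at the site.

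**The concern.** The IRT cannot stratify on a score that does not yet exist. If the stratum is the Day 1 ISLT, the earliest possible randomization is on Day 1 after that test. Section 6.2.4 puts the ISLT late in the session: "At Baseline and on any visits at which both NTB and other cognitive tests are conducted, the NTB should be performed prior". If shipment then follows randomization, the drug cannot be at the center for a Day 1 dose unless it arrives within hours, which the protocol does not mention for its roughly 22 centers in two countries.

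The obvious workaround is to randomize during Screening so that drug has time to arrive. Only the Screening ISLT would then be available, and that is not the named factor. The stratum used could differ from the stratum documented, and sites might resolve this differently. Since this is the only stratification factor, and Section 3.2 relies on it for added balance, the stake would be some of that balance.

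**Working it through.** **Timeline.** Put in order, the statements give: Day 1 ISLT, then IRT assignment, then shipment, then first dose at the center on Day 1. The interval from stratifying score to first dose is Day 1 − Day 1 = 0 days. With any shipping time of one day or more (an assumption; the protocol gives none), the literal sequence cannot be carried out. If the Screening score were used, it could be up to 21 days old, or 35 where a DaTscan, MRI or CT is needed (Table 6-1, footnote a).

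**What early randomization would cost.** The protocol gives no ISLT distribution, retest correlation or practice shift, so this is illustration only. Let the Screening score be N(0, 1) and the Day 1 score N(shift, 1), with correlation ρ and the same raw cut c for both. Write pS and pD for the probabilities of being at or below the cut at each visit, and p11 for both together.

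- Share changing category = pS + pD − 2·p11.
- Share of the chance-imbalance variance in the Day 1 category removed by stratifying on Screening = φ², where φ = (p11 − pS·pD) / √[pS(1−pS)·pD(1−pD)]. This assumes exact balance within Screening strata, so it is an upper bound.

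Example: cut at the median, no shift, ρ = 0.7. Then p11 = 0.3734, the share changing is 0.5 + 0.5 − 2(0.3734) = 0.253, φ = (0.3734 − 0.25)/0.25 = 0.494, and φ² = 0.24.

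| Shift (SD) | Cut (SD from Screening mean) | Changing category, ρ = 0.7 / 0.8 / 0.9 | Variance removed, at most |
|---|---|---|---|
| 0 | 0 | 0.253 / 0.205 / 0.144 | 0.24 / 0.35 / 0.51 |
| 0 | ±1 | 0.149 / 0.122 / 0.086 | 0.19 / 0.29 / 0.46 |
| 0.5 | 0 | 0.289 / 0.253 / 0.215 | 0.21 / 0.29 / 0.38 |
| 0.5 | −1 | 0.135 / 0.120 / 0.103 | 0.14 / 0.22 / 0.31 |
| 0.5 | +1 | 0.224 / 0.197 / 0.168 | 0.18 / 0.26 / 0.36 |

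The range is 0.086 × 80 ≈ 7 to 0.289 × 80 ≈ 23 subjects changing category, with at most 14% to 51% of the variance removed.

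**The same thing as imbalance.** With 40 per arm and half the subjects in each category, the standard deviation of the difference between arms in the Day 1 proportion, without stratification, is about √(0.25 × 2/40) = 0.112. Stratifying on Screening with no shift brings it to 0.112 × √(1 − 0.24) ≈ 0.097 at ρ = 0.7, or 0.112 × √(1 − 0.51) ≈ 0.078 at ρ = 0.9. The alternative to perfect balance is thus ordinary chance imbalance, somewhat reduced.

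**What this touches in the plan.** Section 8.2 makes no formal sample size calculation, so no power figure depends on the stratum. Section 8.5 leaves the model covariates to the SAP. The component lists in Sections 2.1 and 6.2.4.1 do not include the ISLT. One sentence in Section 8.5 mentions episodic memory among the battery's domains but names no test. The ISLT is a secondary endpoint, analyzed as a change.

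**The case for a change.** The strongest case for acting is that this is a contradiction within the protocol and not a detail deferred to the SAP. Baseline means Day 1 wherever it is dated, the stratum is tied to Baseline in four places and never to Screening, and the supply wording points away from site stock. The stratum used for a subject cannot be changed after assignment, so the time to settle it is before the IRT is built, and a clarification would be cheap.

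The textual point stands. The charitable readings, that Baseline is used loosely for the pre-treatment score or that kits are already on site, are possible but nowhere stated. The opening sentence of Section 5.4 does allow randomization once Screening is complete, so early assignment is not foreign to the text, although it does not say which ISLT score then applies.

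The step from there to a needed change does not stand. The harm depends on sites randomizing early, and even then it is limited to balance. Nor is naming the Screening score free of cost. Exclusion criterion 2 in Section 4.2 also applies at Baseline, so early randomization would assign some subjects before that check. Anyone then found ineligible would be randomized but undosed and would fall outside both analysis sets in Section 8.3. Holding drug at the sites has a supply cost that the protocol gives no basis for estimating.

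**Conclusion.** The statements on stratum, shipment and first dose cannot all be followed literally unless drug is delivered the same day. This is a loose end in the operational wording, and no change to the plan follows. The IRT specification and the supply arrangements cannot be completed without fixing the time of randomization, the score entered and the route of the drug, so the gap closes before the first subject is assigned.

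Under either resolution the comparison remains randomized and blinded, and no stated figure, test or conclusion changes. The worst realistic effect is the partial loss of extra balance on one factor, with the alternative being ordinary chance imbalance. The illustrative 9% to 29% of subjects in the other category rests on an assumed bivariate normal model, correlations of 0.7 to 0.9, a cut within 1 SD of the Screening mean and a mean shift of at most 0.5 SD. The only figures here that come from the protocol's own timing are the 0-day interval and the 21- or 35-day Screening window.

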5.5. Study Blinding and Breaking the Blind

Subjects and site personnel associated with study conduct will be blinded to treatment assignment.

During the conduct of the study, the blind should be broken on an individual subject basis in the event of an emergency where it is necessary for the Investigator to know which treatment the subject is receiving before the subject can be treated. The code may also be broken if someone not in the study uses study drug (e.g., if a child in the participant's household takes study drug, the blind may be broken to determine treatment for the child).

When it is necessary to break the blind, the researcher may unblind the treatment immediately (i.e., without prior notice to the Medical Monitor, sponsor, or other) but must notify the Independent Ethics Committee (IEC) per local regulations and Sponsor as soon as possible, preferably by telephone and then in writing, regarding the necessity of code breaking.

If the code is broken for a subject, this must be documented in the electronic case report form (eCRF) and source documents, together with the reasons for breaking the code.

5.6. Dose Modification for Toxicity

No dose modifications are permitted during the study. If a subject is unable to tolerate the assigned study drug dose then the subject should be discontinued from study drug treatment (Section 4.3).

5.7. Prior and Concomitant Therapy

Any medications taken from Screening through the Final Study Visit (i.e. Follow-Up Visit), including all prescription and over-the-counter medications as well as supplements, will be documented in the subject's source document and in the eCRF.

While drug-drug interaction studies have not been conducted, in vitro testing indicates that neflamapimod is metabolized by oxidation in the liver by the cytochrome P450 (CYP) system (combination of CYP3A4

and CYP2C19 isozymes). Until the metabolism is better characterized, **concomitant strong inhibitors of CYP3A4 are prohibited** and **strong inducers of CYP3A4 should be used with caution** in subjects receiving neflamapimod, as the use of such drugs could impact neflamapimod metabolism in subjects who have an underlying CYP2C19 genotypic variant that impacts activity of that CYP2C19.

The following medications are prohibited during study participation:

- Strong CYP3A4 inhibitors (see Table 5-1).
- Any other investigational drug. If a subject has previously participated in a study of an investigational drug, last dosing must have occurred 3 months or 5 half-lives of the investigation drug, whichever is longer, before enrollment in this study.

The Medical Monitor should be contacted with any questions regarding concomitant use of medications that are thought to modulate CYP3A4 activity.

Table 5-1: CYP3A4 Inhibitors

Prohibited: Strong Inhibitors ≥5-fold increase in AUC or >80% decrease in CL	Allowed: Moderate inhibitors ≥2 but <5-fold increase in AUC or 50-80% decrease in CL	Allowed: Weak inhibitors ≥1.25 but <2-fold increase in AUC or 20-50% decrease in CL
boceprevir cobicistat clarithromycin conivaptan danoprevir/ritonavir diltiazem elvitegravir/ritonavir grapefruit juice idelalisib indinavir/ritonavir itraconazole ketoconazole lopinavir/ritonavir nefazodone nelfinavir paritaprevir/ritonavir/ombitasvir posaconazole ritonavir saquinavir/ritonavir telaprevir tipranavir/ritonavir troleandomycin voriconazole	Aprepitant cimetidine ciprofloxacin clotrimazole crizotinib cyclosporine dronedarone erythromycin fluconazole fluvoxamine imatinib tofisopam verapamil	chlorzoxazone cilostazol fosaprepitant istradefylline ivacaftor lomitapide ranitidine ranolazine tacrolimus ticagrelor

Abbreviations: AUC, area under the concentration-time curve; CL, clearance.

Table 5-2: CYP3A4 Inducers

Use with Caution: Strong Inducers ≥80% decrease in AUC	Allowed: Moderate Inducers 50-80% decrease in AUC	Allowed: Weak Inducers 20-50% decrease in AUC				
carbamazepine enzalutamide	bosentan	armodafinil				
mitotane	efavirenz	rufinamide				
phenytoin	etravirine					
rifampin	modafinil					
St. John's wort						

Abbreviations: AUC, area under the concentration-time curve.

5.8. Contraception and Pregnancy

This section should be read in conjunction with the selection criteria that relate to age and contraception:

• Exclusion criteria #10 and #11 (Section 4.2)

No signs of embryo-fetal toxicity or teratogenic effects of neflamapimod were observed in rats. Testing in rabbits was not performed due to lack of exposure following administration of the neflamapimod formulation. No human studies of effects of neflamapimod on conception, pregnancy, or lactation have been performed. Females should not be exposed to neflamapimod if pregnant, breastfeeding, or attempting to conceive. The following guidelines for contraception should be followed from before first dose on Day 1 through 91 days following the last dose of study drug:

Female subjects of child-bearing potential (have not experienced menopause and have not had a hysterectomy or bilateral oophorectomy/salpingo-oophorectomy) or female subjects who have experienced menopause within the previous year must have a negative pregnancy test during Screening and must use at least 1 of the following contraceptive methods: complete abstinence regardless of menstrual cycle timing, contraceptive (oral, transdermal, injectable, or implantable), intrauterine device, or barrier method of contraception.

Male subjects with female partners of child-bearing potential must use at least 1 of the following contraceptive methods: hormonal contraceptives (oral, injectable, patch, intrauterine devices), male sterilization, or total abstinence from heterosexual intercourse, when this is the preferred and usual lifestyle of the subject.

• Abstinence is defined as refraining from heterosexual intercourse during the entire period of risk associated with the study treatments when this is the preferred and usual lifestyle of the subject.

Note that periodic abstinence (calendar, symptothermal, post-ovulation methods), withdrawal (coitus interruptus), spermicides only, and lactational amenorrhoea method are not acceptable methods of contraception.

Any pregnancy should be reported to the Investigator, and, in turn, the pregnancy should be reported to Worldwide Clinical Trials within 24 hours of the Investigator's awareness of the pregnancy. If a female

subject becomes pregnant, study drug will be permanently discontinued and the subject will be discontinued from the study.

With proper informed consent (separate pregnancy informed consent form), the subject or partner will be followed through the completion of the pregnancy and outcome of the pregnancy reported, and the infant will be followed for 12 months after birth.

5.9. Treatment Compliance

Treatment compliance will be assessed by reviewing the count of returned capsules at each visit. Any apparent discrepancies between quantity of capsules returned and the number expected based on dosing schedule will be discussed with the subject to ensure an understanding of dosing instructions.

Repeated non-compliance with dosing instructions may necessitate discontinuation from the study, based on the Investigator's judgment (Section 4.3).

6. STUDY ASSESSMENTS AND PROCEDURES

6.1. Schedule of Assessments

The schedule of assessments is presented in Table 6-1.

Table 6-1: Schedule of Assessments

	Study Period / Week / Study Day								
								Early	Follow-
	Screening		7	Freatmen	t Period			Termination	Up
	Screening Visit ^a	Baseline	Week 2	Week 4	Week 8	Week 12	Week 16	ET Visit ^e	Follow- Up Visit ^d
Assessment	Within 21- 35 days of D1	D1 ^b	D14	D28	D56	D84	D112	Within 3 days after last dose	Within 14 days (±3) of last dose
Informed Consent	Xe	DI:	(±3)	(±3)	(±5)	(±5)	(±5)		iast dose
	X								
Medical history review	X X ^f								
Pregnancy testing	X						v	v	v
Physical examination ^g Vital signs ^h	X	X	X	X	X	X	X	X	X
Hematology and	X	X	Λ	X	X	X	X	X	Λ
chemistry ⁱ	Λ	A		Λ	Λ	Λ	Λ	Λ	
Coagulation studies ⁱ	X				X				X
12-lead electrocardiogram ^j	X								
DaTscan TM , if needed	X^k								
CT/MRI	X¹								
C-SSRS	X	X		X	X	X	X	X	
MMSE ^m	X	X			X		X	X	
NTB ^m , International Shopping List Test (ISLT)	X	X		X	X		X	X	
CDR-SB		X			X		X	X	
NPI-10	X	X		X	X		X	X	
Timed Up and Go (TUG)		X			X		X	X	
EEG ⁿ		X					X	X	
Dispense study drug		X	X	X	X	X			
Pharmacokinetic sampling ^o			X	X	X				
Plasma sample for protein biomarker testing ^p	X^q	X					X	X	

	Study Period / Week / Study Day								
	Screening	Treatment Period						Early Termination	Follow- Up
	Screening Visit ^a	Baseline	Week 2	Week 4	Week 8	Week	Week 16	ET Visit ^e	Follow- Up Visit ^d
	Within 21-							Within 3 days after	Within 14 days
Assessment	35 days of D1	D1 ^b	D14 (±3)	D28 (±3)	D56 (±5)	D84 (±5)	D112 (±5)	last dose	(±3) of last dose
Prior/concomitant medication	X	X	X	X	X	X	X	X	X
Adverse event recording	X	X	X	X	X	X	X	X	X
Final study drug reconciliation							X	X	

CDR-SB: Clinical Dementia Rating Scale – Sum of Boxes; C-SSRS: Columbia-Suicide Rating Scale; CT: Computed tomography; D=day; MMSE: Mini-Mental State Examination; MRI: Magnetic resonance imaging; NPI-10: 10-item Neuropsychiatric Inventory; NTB: Neuropsychological Test Battery.

- a. One to two Screening visits are planned during which safety screening procedures are to be completed and reviewed, including a practice NTB and the required diagnostic and cognitive impairment procedures. Screening will be conducted within 21 days before Baseline (Day 1); if a DaTscan and/or MRI or CT scan is required to determine study eligibility, Screening may be extended to 35 days. (If necessary, a second visit may be conducted on a different day to allow for scheduling purposes.) All screening assessments should be conducted within 21-35 days of Day 1 and can be condensed to one visit
- b. On Day 1, all procedures should be conducted prior to first dose of study drug.
- c. Subjects who prematurely discontinue study drug for any reason will be asked to return to the study center for an Early Termination visit within 3 days following the last study drug dose; if it is determined that the subject will discontinue study drug while at the study center for a scheduled visit, then the Early Termination visit should be conducted at that time.
- d. The Follow-up Visit should be conducted within 14 (±3) days of the last dose of study drug for subjects who complete the study or discontinue early.
- e. Informed consent procedures, including signing of informed consent, must be completed before any study-specific procedures are performed.
- f. Female subjects who have reached menopause in the previous year must have a serum or urine pregnancy test performed during Screening; subjects with positive results are not eligible for study participation.
- g. Refer to Section 6.2.8 for details regarding physical examination.
- h. Vital signs include blood pressure, pulse, respiratory rate, and body temperature. Vital signs should be measured after the subject has been in sitting position for 5 minutes.
- i. Details of clinical laboratory sampling for chemistry, hematology, and coagulation studies are discussed in Section 6.2.10.
- j. Details of 12-lead ECG assessment are discussed in Section 6.2.9.
- k. Subjects are required to have a prior DaTscan. If a DaTscan has not been performed within the previous 2 years, it is to be performed during Screening only after subject has been deemed eligible based on all other inclusion/exclusion criteria (e.g., medical history, laboratory testing) and prior to randomization. Note that if DaTscan results are negative (i.e., no evidence of

- reduced uptake in the basal ganglia), the subject is required to have historical PSG-verified RBD to be eligible for study participation.
- 1. If MRI or CT has not been performed within 3 years before Screening and/or results are not available, MRI or CT scan must be performed to exclude other disease as part of Screening only after subject has been deemed eligible based on all other inclusion/exclusion criteria (e.g., medical history, laboratory testing) and prior to randomization (see Section 6.2.2).
- m. Refer to Section 6.2.4 for details regarding cognitive function tests.
- n. EEG need not performed at the ET visit for subjects who discontinue prior to Week 4 (Day 28).
- o. Refer to Section 6.2.11 for details regarding PK sampling.
- p. Refer to Section 6.2.12 for details regarding plasma biomarker sampling.
- q. Only plasma Aβ42/40 ratio is required at Screening.

